#### 9.7.4 Meta-analysis

After evaluating potential treatment effect heterogeneity we may pool results from the two databases. Descriptive tables and all parameter estimates from the main and all sensitivity analyses will be pooled using meta-analytic methods assuming a fixed effects model, since random effects pooling can be biased in the context of few databases [R17-1410]. Calculation of an overall mean/proportion/hazard ratio from two databases reporting a single mean/proportion/hazard ratio will use the inverse variance method for pooling [R02-0971].

To correct variance for potential duplicates in pooling two databases for the primary outcome, the following method will be used. The variance correction for overlapping samples when pooling multiple databases was described by [REDACTED] and [REDACTED] [M20-0016].

[figure not shown]
The formula for the variance is given by

$$\hat{\sigma}_{combined}^2 = w_1^2 \hat{\sigma}_1^2 + w_2^2 \hat{\sigma}_2^2 + 2w_1 w_2 \rho \hat{\sigma}^2$$

Where

- $w_1$  and  $w_2$  are the weights applied to the two databases and  $w_2 = 1 - w_1$
- $\hat{\sigma}_1^2$  and  $\hat{\sigma}_2^2$  are the variance estimates from both databases
- $\rho$  is the % of overlapping observations in the smaller dataset
- $\hat{\sigma}^2 = (n_1 \hat{\sigma}_1^2 + n_2 \hat{\sigma}_2^2) / 2$  where  $n_1$  and  $n_2$  are the number of observations in both databases

Given that an exact overlap is not known between databases, estimates in 10% intervals will be used to assess varying degrees of variance in the pooled point estimates. The pooled analyses will be conducted using R package **rmeta** in R studio [R20-1986, M20-0016].

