## **9.5 STUDY SIZE**

All patients with T2DM who newly initiate therapy with empagliflozin or study comparator who meet the inclusion and exclusion criteria will be included in the analysis.

Event rate of acute pancreatitis reported in patients with T2DM who are treated with canagliflozin was reported to be 2.2 per 1000 PY [\[RRA-21430\]](#). This rate was used for sample size calculation using the formula of Farrington and Manning (maximum likelihood method) [\[R14-3295\]](#).

Null hypothesis H0:  $\pi_2 / \pi_1 \geq 1.5$  (non-inferiority)

A single stage (fixed sample size) design was chosen.

For specified  $\alpha = 0.05$  and rates  $\pi_1 = 0.0022$  and  $\pi_2 = 0.0022$  (odds ratio of 1.000) the power (1 -  $\beta$ ) is 80.0% if the test stages consist of the sample sizes given in the last two columns of [Table 1](#).

The computation assumes an allocation ratio (n2/n1) = 1 (Table 1). It is assumed that all patients have 1 year of follow up.

**Table 1** Number of empagliflozin initiators and empagliflozin-exposed person-years needed to detect a HR of 1.5 and 2.0 with a power of 80% and  $\alpha = 0.05$  under 1:1 matching ratio

Hazard ratio (HR)	Information rate	Bunds accept $H_0$	Bunds reject $H_0$	sign.level one-sided	$\alpha$ spent	$\beta$ spent	power achieved	Observations per exposure group	Overall observations
1.5	1.0	1.645	1.645	0.0500	0.0500	-	0.8000	34585.4	69170.8

ADDPLAN Adaptive Design Software 2019 and SAS 9.4 software ( ) were used to calculate the sample size.

Analysis of this study will be initiated as soon as a sufficient sample size to exclude a HR of 1.5 with 80% power is reached. Based on a feasibility assessment conducted in Optum and MarketScan databases using data between 1 August 2014 and the latest data-cut available in MarketScan (30 September 2020) and Optum (31 March 2021), the dual-therapy cohort was reported with the highest number of empagliflozin initiators, therefore meta-analysis of the dual therapy cohorts including the data from the MarketScan and Optum databases will be the main analysis of this study as it will be the only powered analysis.

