For patients who add an incretin-based therapy, SGLT2i, or a within treatment line comparator index drug, their data will be censored on the date of the prescription claim for the added medication.

Patients with chronic use of insulin at baseline (see SEAP for definition) in the outpatient setting during the follow-up period will be censored from the study.

From a feasibility assessment conducted in November 2021, it is known that there are not enough study participants in the Optum and MarketScan database in each therapy line and the dual-therapy cohort was reported with the highest number of empagliflozin initiators. Therefore, a meta-analysis of the dual therapy cohorts including the data from the Marketscan MarketScan and Optum databases will be the main analysis of this study

Meta-analysis of different treatment line cohorts with the different comparators (first, second and third line) will not be conducted in this study as patients in these 3 cohorts will likely have very different profiles including different disease stages, and results would be difficult to interpret.

The incidence rates (per 1000 PY) and corresponding 95% confidence intervals (CI) of acute pancreatitis during the follow-up time will be calculated in each exposure group of interest in the unmatched and PS-matched cohorts.

All results will be presented for each database separately but if there is not enough sample size in each treatment line cohort in each database, after evaluating potential heterogeneity, meta-analysis techniques will be used to pool the 2 treatment line cohorts of the 2 databases. Descriptive tables and all parameter estimates from the main and all sensitivity analyses will be pooled using meta-analytic methods assuming a fixed effects model, to avoid potential biases associated with random effects pooling in the context of few databases [R17-1410].

Cox proportional hazards regression models based on time-to first acute pancreatitis event will be used to estimate hazard ratios (HR) and 95% CIs for each treatment line comparison of interest (in each database or in case of limited sample size a meta-analysis of 2 databases) in the unmatched and PS-matched cohorts. Proportionality hazard assumption will be checked using the log rank test.

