## **9.9.5 Generalizability**

Using a PS-matched analysis within a new user active comparator design decreases channelling bias, but also decreases the representativeness of the final patient cohort. The findings might not be generalizable to all patients with T2DM, especially those on treatment regimens that will not be included in this analysis.

The use of large claims data sources, such as MarketScan and Optum CDM, helps to ensure good representativeness of the US population. Although people over 65 years are under-represented in the MarketScan databases, the use of the Optum CDM data will increase the proportion of people older than 65 years in the analysis.

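### Inverse-variance pooling, with no scale stated, is unsuited to the pooled proportions and incidence rates: they depart from the plain totals whenever the two databases differ

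*Protocol*

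**What the plan says.** Protocol 9.7.4 sets one rule for everything that is pooled: "Descriptive tables and all parameter estimates from the main and all sensitivity analyses will be pooled using meta-analytic methods assuming a fixed effects model". It then gives the method: an overall figure "from two databases reporting a single mean/proportion/hazard ratio will use the inverse variance method for pooling". Section 9.7.3 repeats the general sentence. Neither place says whether pooling is on the natural, log, logit or another scale. SAP 10.4 only refers back to the protocol.

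Incidence rates are not in the list of mean, proportion and hazard ratio. They are a planned output of 9.7.3 ("The incidence rates (per 1000 PY) and corresponding 95% confidence intervals (CI) of acute pancreatitis during the follow-up time will be calculated", per exposure group, unmatched and matched). They come under 9.7.4 only as part of the descriptive tables and parameter estimates, and no other pooling rule is given for them.

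The check before pooling concerns the treatment effect: "After evaluating potential treatment effect heterogeneity we may pool results from the two databases". Section 9.7.3 also has all results presented for each database separately.

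**The concern.** Inverse-variance weights suit a log hazard ratio, where the variance mainly reflects the number of events. For a rate or a proportion the variance is a function of the estimate. One database then gains or loses weight because its rate happens to be low or high, and not only because of its size.

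The abstract and SAP 5 state the objective as comparing incidence rates, so pooled arm-specific rates and a pooled baseline table will be read beside the hazard ratio. The weights also differ by arm, so the two pooled arm rates can refer to different mixes of the databases. The heterogeneity check would not reveal this: equal hazard ratios can go with quite different background rates or baseline proportions. The documents expect the populations to differ in at least one respect, since "people over 65 years are under-represented in the MarketScan databases".

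**Working it through.** **The plan's own figure.** The documents state no pooled rate. The related figure is the sample size in 9.5. With p = 0.0022 in both groups, margin R = 1.5, one-sided alpha 0.05 and 80% power, the Farrington-Manning formula is

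n = [z(0.95)·√v0 + z(0.80)·√v1]² / (p − Rp)²,

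with v0 = Rq(1 − Rq) + R²q(1 − q), v1 = p(1 − p) + R²p(1 − p), and constrained estimate q = 0.0017598. It gives 34,585.41 per group, matching the stated 34585.4. At one year each, that is 34,585.4 × 0.0022 = 76 events per group.

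**Inputs.**
- Planning rate 2.2 per 1000 PY, from a canagliflozin cohort (9.5: "treated with canagliflozin was reported to be 2.2 per 1000 PY").
- US claims rates in type 2 diabetes of 4.22 to 5.60 per 1000 PY (section 7).
- Laboratory results available for 40-50% of Optum and 5-15% of MarketScan patients (9.3.3; 9.9.1 says about 5% for MarketScan).
- Share of person-years or patients by database: not given. Assumed equal, with 30:70 and 70:30 as the range.

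**Rates.** With d events in T person-years, r = d/T.
- Natural scale: variance d/T², weight T²/d = T/r, pooled rate ΣT / Σ(T/r). This is the harmonic mean when the T are equal.
- Log scale: variance 1/d, weight d.
- Square-root scale: weight proportional to T.
- Reference: Σd / ΣT.

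For 2.2 and 4.22 with equal T, the natural scale gives 2/(1/2.2 + 1/4.22) = 2.89, and the reference is (2.2 + 4.22)/2 = 3.21.

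| Database rates per 1000 PY | Ratio | Reference | Natural scale | Log scale | Square-root scale |
|---|---|---|---|---|---|
| 4.22 and 5.60 | 1.33 | 4.91 | 4.81 (−2.0%) | 4.96 (+1.0%) | −0.5% |
| 2.2 and 3.3 | 1.50 | 2.75 | 2.64 (−4.0%) | 2.81 (+2.0%) | −1.0% |
| 2.2 and 4.22 | 1.92 | 3.21 | 2.89 (−9.9%) | 3.38 (+5.2%) | −2.5% |
| 2.2 and 5.60 | 2.55 | 3.90 | 3.16 (−19.0%) | 4.30 (+10.3%) | −5.0% |

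On the natural scale the equal split is the worst case: at 30:70 or 70:30 the last two rows become −8.4% and −16.5%. On the log scale the last row reaches +11.2% when 70% of person-years are in the lower-rate database.

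If the true rates are equal, only chance separates the databases. In 1,000,000 simulated Poisson draws at the planned size, the natural-scale rate is low by 1.3% on average, and by more than 10% in 0.6% to 0.8% of studies. With half the person-years these become 2.7% and 5% to 6%.

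**Proportions.** Natural-scale weight n/(p(1 − p)); logit-scale weight n·p(1 − p). Here the documents supply the gap and only the size split is assumed. Because 9.7.7 adds a missing category for partly missing variables, laboratory availability becomes a table proportion. For 45% and 10% with equal n:
- Natural: weights 1/(0.45 × 0.55) = 4.04 and 1/(0.10 × 0.90) = 11.11; pooled (4.04 × 0.45 + 11.11 × 0.10)/15.15 = 19.3%.
- Logit: weights 0.2475 and 0.0900, logits −0.201 and −2.197; pooled logit −0.733, which is 32.5%.
- Reference: 27.5%.

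The smallest gap (40% and 15%) gives 23.7% on the natural scale and the largest (50% and 5%) gives 12.2%, each against 27.5%. For 45% and 10% the natural-scale error is −28% with 30% of patients in Optum and −24% with 70%.

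**Categories.** Each band gets its own weights, so pooled bands need not total 100%. With the four age bands of SAP Annex 3, equal n and assumed mixes of 50/40/7/3% and 25/25/30/20%, the natural-scale bands pool to 35.7, 31.6, 12.4 and 5.6%, a total of about 85%. Milder assumed mixes (45/35/12/8% and 30/27/26/17%) total 96%.

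**Zero counts.** If a covariate has no patients in one database, p(1 − p) = 0 and the natural-scale weight is undefined. SAP Annex 3 lists individual drugs that may be rarely dispensed, so this can happen.

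**Means.** The weight is n/s². The pooled mean departs from the N-weighted mean when the standard deviations differ as well as the means.

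**The case against.** A reader might infer that the pooled pancreatitis rate will be 10% to 19% too low. The documents do not support that.
- No scale is stated, and the sign depends on it: upward on the log scale, and upward on the natural scale for proportions above 50% (90% and 95% pool to 93.3% against 92.5%).
- The method's reference entry includes a paper on meta-analysis of prevalence, so a transformation may be intended. The published text around 9.7.4 also has gaps.
- Rates enter only by implication.
- The 10% and 19% set a canagliflozin-cohort rate against diabetes-population rates from other studies, as if each came from one of these databases. Within the quoted US claims range the error is 2%. A different age mix does not by itself show that pancreatitis rates differ.

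All of this stands, and it limits the direction and size that can be claimed. It does not rescue the rule: on the natural, log or logit, and square-root scales alike, the result misses the plain total when the databases differ.

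A second possible inference is that the main result is biased. It is not: the powered analysis is the pooled dual-therapy hazard ratio, for which inverse variance on the log scale is suitable. Separate database results also remain visible.

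Third, a fixed-effect model targets one assumed common value, whereas totals give a size-weighted average. That is a fair distinction. But a baseline table is meant to describe the patients studied, and with no common value the inverse-variance mix describes no particular population.

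Fourth, summing has a cost. Protocol 9.9.1 estimates 10-15% overlap between the databases, expects less in the study population, and cannot remove duplicates. For two equal databases with overlap ρ, the variance of the average is (σ²/2)(1 + ρ). An ordinary Poisson interval therefore has a standard error too small by a factor √(1 + ρ), which is 1.05 at 10% and 1.07 at 15%. This stands and shapes the fix.

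**Conclusion.** The concern holds for pooled proportions, which 9.7.4 names, and by implication for pooled incidence rates. For rates with equal person-years, the natural-scale error is about −2% for a 1.3-fold gap between databases and −10% to −19% for a 1.9- to 2.5-fold gap; the log-scale error over the same gaps is about +1% to +10%. Which gap applies is unknown, and the error is zero if the observed rates agree. The firmest example is laboratory availability, where the documents themselves give very different proportions: 19.3% or 32.5% against 27.5%, assuming equal n. Natural-scale categories that fail to total 100%, and zero counts without a usable weight, are practical faults of the same rule. The defect is confined to descriptive rates, proportions and means. It should be corrected, but it does not threaten the pooled hazard ratio.

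**What to change.** In 9.7.4, with a matching sentence in SAP 10.4:
- Restrict inverse-variance pooling to the log hazard ratio, and name the log scale.
- Pool incidence rates as total events over total person-years in each arm, proportions as total count over total N, and means as N-weighted means.
- Keep the database-specific columns.
- Give the pooled rate a Poisson-based 95% interval, with its variance widened over the same overlap scenarios (0%, 10%, 20% and so on) that are planned for the primary outcome.

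The cost is a few sentences. The sponsor holds both data sets, so the point estimates become simpler to program. The small downside is that summing counts overlapping patients twice; the widened interval deals with this for the pooled rate, and a table note should say so for the descriptive counts.

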### **9.9.1 Data source**

The source claims data include limitations with respect to certainty of the capture of exposure, covariates, and outcomes. As a comprehensive insurance database, essentially all billable medical services will result in claims for reimbursement, so that the certainty of capture is tied to likelihood of a claim being submitted to the insurer.

Although duration of diabetes may represent a risk factor for the study outcome, this covariate will be incompletely captured since the patient history in the dataset is relatively short (at least 12 months, and an average of approximately 2 years), and a first claim within the database may not represent diabetes onset since the condition can be latent for some time and is typically not treated with hypoglycaemic medications at its diagnosis.

New initiators are operationally defined as patients with no use in the prior 6 months. This does not ensure, however, that patients have never used the drug of interest; the possibility remains that these patients were treated at some prior time point before they enrolled in their insurance plan.

There is potential for misclassification of dose based on healthcare utilization data, but the “days supply” field is expected to be fairly accurate. Similar concern may be present for exposure classification as well, but we expect the drug codes utilized in the data sources will appropriately represent the drug that is being classified.

Medication use in administrative healthcare databases is restricted to prescription drug medication. Consequently, the use of over-the counter (OTC) medications (e.g., OTC aspirin) is not captured. Additionally, the indication of a claim for prescription medications does not confirm whether the medication was actually taken by the patient or taken as prescribed.

It is estimated that two databases (MarketScan and Optum CDM) have about 10-15% overlap and it is not possible to identify duplicates and remove them between the two databases because patients are de-identified. It is not expected that this overlap impacts the results of this study because it will be much smaller in the study population. Furthermore, there is a sensitivity analysis to consider several scenarios of overlap in patients between the MarketScan and Optum (e.g., 0%, 10%, 20%, etc.), and 95% CIs of primary outcome will be adjusted accordingly.

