10.4 META-ANALYSIS

Please check study protocol section 9.7.4.

BOEHRINGER INGELHEIM Group of Companies
Statistical and Epidemiological Analysis Plan (SEAP) for Non-
Interventional Studies (NIS)

c37922104-02

Page 13 of 27

Proprietary confidential information © 2022 Boehringer Ingelheim International GmbH or one or more of its affiliated companies

BOEHRINGER INGELHEIM Group of Companies
Statistical and Epidemiological Analysis Plan (SEAP) for Non-
Interventional Studies (NIS)

c37922104-02

Page 14 of 27

Proprietary confidential information © 2022 Boehringer Ingelheim International GmbH or one or more of its affiliated companies

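### The overlap-corrected pooled variance in Protocol 9.7.4 lacks a division by sample size in its covariance term, so every non-zero overlap scenario gives an unusable confidence interval

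*Protocol*

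**What the plan says.** Protocol 9.7.4 pools the two databases with fixed-effect inverse-variance weights and then states: "To correct variance for potential duplicates in pooling two databases for the primary outcome, the following method will be used". Writing s1 and s2 for the two database variance estimates, the combined variance is

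V = w1²·s1 + w2²·s2 + 2·w1·w2·ρ·S, with S = (n1·s1 + n2·s2)/2.

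Here ρ is the overlap as a share of the smaller dataset, and the definition of S ends with the divisor "2$ where $n_1$ and $n_2$ are the number of observations in both databases". Because the true overlap is unknown, "estimates in 10% intervals will be used to assess varying degrees of variance in the pooled point estimates".

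Protocol 9.9.1 relies on this. "It is estimated that two databases (MarketScan and Optum CDM) have about 10-15% overlap", duplicates cannot be removed, and under the overlap scenarios "95% CIs of primary outcome will be adjusted accordingly". SAP 10.4 adds nothing of its own: "Please check study protocol section 9.7.4". Protocol 9.5 makes the two-database meta-analysis of the dual-therapy cohorts the main and only powered analysis.

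**The concern.** The first two terms are the usual variance of a weighted average of independent estimates, so s1 and s2 must be squared standard errors. Then n·s is a per-observation variance, S is the mean of two of these, and the covariance term is too large by a factor of about the sample size.

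A limiting case shows this without trial data. Take two identical databases with full overlap: n1 = n2 = n, s1 = s2 = s, w1 = w2 = ½, ρ = 1. Pooling a dataset with itself adds no information, so V should equal s. The printed formula gives s/2 + n·s/2.

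The formula governs the confidence interval for the primary outcome in the main analysis. If analysts find the output impossible, they would have to choose a repair after seeing results.

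**Working it through.** **Inputs.** From Protocol 9.5: 69,170.8 patients overall (34,585.4 per exposure group), event probability 0.0022 in both groups, one year of follow-up, margin 1.5, one-sided α 0.05. Assumptions not in the documents: an equal database split (60/40 and 70/30 as alternatives), true HR 1, and Var(log HR) = 4/events.

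**The plan's own figure.** The Farrington–Manning calculation for a ratio of 1.5, one-sided 5%, 80% power and 1:1 allocation gives 34,585.4 per group, as in Table 1. Expected events: 69,170.8 × 0.0022 = 152.2, or 76.1 per database.

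**No overlap.** s1 = s2 = 4/76.09 = 0.0526. V = 0.25 × 0.0526 + 0.25 × 0.0526 = 0.0263. SE 0.162; upper 95% limit exp(1.96 × 0.162) = 1.37.

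**As printed.** S = (34,585.4 × 0.05257 + 34,585.4 × 0.05257)/2 = 1,818. At ρ = 0.10, the third term is 2 × 0.25 × 0.10 × 1,818 = 90.9.

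**Correctly scaled.** If ρ·n_smaller patients are shared, the covariance of the two estimates is n_overlap·S/(n1·n2) = ρ·S/n_larger. At ρ = 0.10, the third term is 90.9/34,585 = 0.00263, so V = 0.0289.

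| Overlap | SE, printed | SE, scaled | Upper 95% limit, scaled |
|---|---|---|---|
| 0% | 0.162 | 0.162 | 1.37 |
| 10% | 9.54 | 0.170 | 1.40 |
| 15% | 11.7 | 0.174 | 1.41 |
| 20% | 13.5 | 0.178 | 1.42 |

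The printed formula's 95% interval at 10% runs from about 7.6 × 10⁻⁹ to 1.3 × 10⁸. With 60/40 and 70/30 splits the printed SE at 10% is 9.34 and 8.74, and the scaled SE is 0.1685 and 0.1669. In the full-overlap case the printed V is 0.0526/2 + 1,818/2 = 909, against a correct 0.0526.

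**Simulation.** With 6,000 and 3,000 patients per group in the two databases and 20% overlap, the empirical covariance was 0.00128. ρ·S/n_larger gives 0.00128; the printed term gives 15.3.

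**Other readings, equal split, 10% overlap.**
- n as patients per arm: SE 6.7.
- n as events: SE 0.48, upper limit 2.54.
- s1 and s2 as per-observation variances: the 0% step already fails, since V = 1,818/2 = 909 and SE is about 30. Repair would then need the first two terms divided by n1 and n2, the 2 under S replaced by n1 + n2, and the covariance divided by the larger n.
- ρ entered as 10 rather than 0.10: worse still.

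**Effect of overlap itself.** With correct scaling, the variance is multiplied by 1 + 2·ρ·(share of the smaller database): 1.10 at 10% and 1.15 at 15% for an equal split, 1.06 and 1.09 for 70/30. Power is Φ(ln 1.5/SE − 1.645):
- no overlap: Φ(0.4055/0.1621 − 1.645) = 80.4%;
- 10%: 77.0% (78.4% at 70/30);
- 15%: 75.4% (77.3% at 70/30).

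Restoring the no-overlap precision needs 69,171 × 1.06 to 1.10, about 73,300–76,100 patients, at 10%, and × 1.09 to 1.15, about 75,400–79,500, at 15%.

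**The case against.** The algebra is hard to dispute, so the case on the other side concerns provenance and weight.

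- **A divisor may have been lost.** The text available here was extracted from a PDF, a figure just before the formula is not shown, and M20-0016 is unpublished. This cannot be excluded, so checking the source comes first. However, the formula and the separate definition of S lack the divisor consistently.
- **The error would reveal itself.** Limits near 10⁻⁸ and 10⁸ would not pass the independent double programming and quality control in Protocol 9.8. That makes a silent wrong conclusion unlikely, but it leaves no prespecified replacement. If n were taken as events, an upper limit of 2.54 would look plausible and still be wrong.
- **It is only a sensitivity analysis.** Protocol 9.9.1 uses that label, but 9.7.4 prescribes the correction for the primary outcome.
- **The power loss comes from overlap, not from the formula.** This is right. It also applies only if 10–15% holds in the study cohort and the cohort is no larger than the required size; the documents do not give the feasibility counts.
- **The 10–15% refers to the whole databases.** Protocol 9.9.1 continues: "It is not expected that this overlap impacts the results of this study because it will be much smaller in the study population". It gives no figure and does not say whether count or proportion is meant; the formula uses the proportion. This is a secondary gap, and the formula error does not depend on it.

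**Conclusion.** The concern holds. As printed, the covariance term is on the wrong scale, and no reading consistent with the stated definitions rescues it. At the planned size, the 10% step gives an SE of 9.5 where 0.170 is right. The size of the error depends on the assumed database split, the 4/events approximation and the meaning of n; its existence does not.

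The pooled estimate and the 0% interval are unaffected. The proper correction is modest: at HR 1 the upper limit stays below 1.5 up to 20% overlap. If 10–15% overlap does hold in the cohort, power at the planned size falls somewhat below the level in the protocol's trigger for starting analysis, "a sufficient sample size to exclude a HR of 1.5 with 80% power is reached". This must be fixed before any overlap-adjusted interval is computed.

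**What to change.** 1. Check the formula in Protocol 9.7.4 against M20-0016 and correct it. The preferred form is V = w1²·s1 + w2²·s2 + 2·w1·w2·ρ·S/max(n1, n2), with S = (n1·s1 + n2·s2)/2 unchanged and ρ a fraction between 0 and 1. This matches the definition of ρ on the smaller dataset. Replacing the 2 under S by n1 + n2 is an acceptable approximation: it is identical when n1 = n2, and within 0.002 on the SE at 10% and 0.003 at 15% for splits up to 70/30.
2. State that s1 and s2 are variances of the log HR estimates, and whether n counts patients, patients per arm or events.
3. State the assumption that overlapping patients contribute the same data in both databases.
4. Report the 10% and 20% scenarios beside the primary confidence interval.
5. While editing, clarify in 9.9.1 whether the smaller overlap expected in the cohort is a proportion, and on what basis.

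The cost is one formula and a few sentences in the protocol. The SAP inherits the change by reference, and no new data are needed.
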